7.2.5.2. Secondary Endpoints

Secondary endpoints are described in Section 2.

KCCQ-OS will be analyzed using a similar MMRM model as used for the primary endpoint.

The composite endpoint of all-cause mortality, frequency of CV-related hospitalizations and change from baseline in 6-MWT will be analyzed using a generalized rank-based win ratio method, which makes pairwise comparisons (for all possible patisiran/placebo patient pairs) of the 3 components in the hierarchical order specified above. The point estimate for the win ratio is defined as the total number of better outcomes divided by the total number of worse outcomes in the patisiran group. The detailed algorithm for assessment of this endpoint will be provided in the SAP.

The composite endpoint of all-cause mortality and all-cause hospitalizations will be analyzed using an Andersen-Gill model stratified by baseline tafamidis (yes vs no), including treatment, genotype (hATTR vs wtATTR), NYHA Class (I/II vs III), and age (<75 vs \geq 75 years) as covariates.

Patients who undergo a heart transplantation and/or ventricular assist device placement after randomization will be handled in the same manner as death in the primary analyses of mortality related endpoints.

To control the overall Type I error rate, secondary endpoints will be tested in a prespecified hierarchical order.

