2. OBJECTIVES AND ENDPOINTS

Objectives	Endpoints
Primary	
To evaluate the efficacy of patisiran compared with placebo treatment on functional capacity (6-minute walk test [6-MWT]) in patients with ATTR amyloidosis with cardiomyopathy	Change from baseline at Month 12 in 6-MWT
Secondary	
To evaluate the efficacy of patisiran compared with placebo treatment on: 
 • Health status and health-related quality of life • Patient mortality and hospitalizations 	
 • Change from baseline at Month 12 in Kansas City Cardiomyopathy Questionnaire Overall Summary (KCCQ-OS) score • Composite endpoint of all-cause mortality, frequency of cardiovascular (CV)-related hospitalizations and change from baseline in 6-MWT over the 12-month double-blind period • Composite endpoint of all-cause mortality and frequency of all-cause hospitalizations over the 12-month double-blind period
Exploratory	
To evaluate the efficacy of patisiran compared with placebo treatment on: 
 • All-cause mortality and CV-related hospitalizations • Cardiac biomarkers and biomarker-based risk assessment • Manifestations of cardiac amyloid involvement 	
 • Composite endpoint of all-cause mortality and frequency of CV-related hospitalizations over the 12-month double-blind period • Change from baseline at Month 12 in: 
 ◦ N-terminal prohormone B-type natriuretic peptide (NT-proBNP) ◦ ATTR amyloidosis disease stage • Change from baseline at Month 12 in: 
 ◦ New York Heart Association (NYHA) Class ◦ Echocardiographic parameters ◦ Modified body mass index (mBMI)

Objectives	Endpoints
	
 ○ Cardiac magnetic resonance (CMR) parameters ○ Technetium scintigraphy parameters ○ Troponin I levels ○ Norfolk QoL-DN
Pharmacodynamics (PD) and Pharmacokinetics (PK)	

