3. Medical history of HF with at least 1 prior hospitalization for HF (not due to arrhythmia or a conduction system disturbance treated with a permanent pacemaker) **OR** clinical evidence of HF (with or without hospitalization) manifested by signs and symptoms of volume overload or elevated intracardiac pressures (eg, elevated jugular venous pressure, shortness of breath or signs of pulmonary congestion on x-ray or auscultation, peripheral edema) that currently requires treatment with a diuretic.
4. Patient meets one of the following criteria:
 - a. Tafamidis naïve; in addition to patients who have never taken tafamidis, those who have been on tafamidis for ≤30 days total and have not received any tafamidis in the 6 months prior to baseline will be considered tafamidis naïve and may qualify for the study.
 - b. Currently on tafamidis (for ≥6 months) and has demonstrated disease progression, as determined by the Investigator. (At the time of study entry, tafamidis treatment must be on-label use of commercial tafamidis.)
5. Patient is clinically stable, with no CV-related hospitalizations within 6 weeks prior to randomization, as assessed by the Investigator.
6. Able to complete ≥150 m on the 6-MWT at screening.
7. Screening NT-proBNP >600 ng/L and <8500 ng/L.

Informed Consent

8. Patient is able to understand and is willing and able to comply with the study requirements and to provide written informed consent; and patient agrees to sign the medical records release form for collection of vital status.

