4.2. Exclusion Criteria

Patients are excluded from the study if any of the following criteria apply:

Disease-specific Conditions

1. Has known primary amyloidosis (AL) or leptomeningeal amyloidosis.

2. NYHA Class III **AND** ATTR amyloidosis disease Stage 3 (defined as both NT-proBNP >3000 ng/L and estimated glomerular filtration rate [eGFR] <45 mL/min/1.73 m^2).[\[Gillmore 2018\]](#)
3. NYHA Class IV at the Screening visit.
4. Has a polyneuropathy disability (PND) Score IIIa, IIIb, or IV (requires cane or stick to walk, or is wheelchair bound) at the Screening visit.

Laboratory Assessments

5. Has any of the following laboratory parameter assessments at screening:
 - a. Aspartate transaminase (AST) or alanine transaminase (ALT) levels $>2.0 \times$ the upper limit of normal (ULN).
 - b. Total bilirubin $>$ ULN. Patients with elevated total bilirubin that is secondary to documented Gilbert's syndrome are eligible if total bilirubin $<2 \times$ ULN.
 - c. International normalized ratio (INR) >1.5 (unless patient is on anticoagulant therapy, in which case excluded if INR >3.5).
6. Has eGFR <30 mL/min/1.73 m^2 (using the modification of diet in renal disease [MDRD] formula).
7. Has known human immunodeficiency virus infection; or evidence of current or chronic hepatitis C virus or hepatitis B virus infection.

Prior/Concomitant Therapy

8. Tafamidis naïve patients (at baseline) for whom the Investigator actively plans or anticipates commencing treatment with tafamidis during the 12-month double-blind period, taking into consideration clinical status, patient preference and/or commercial availability of tafamidis.
9. Is currently taking diflunisal; if previously on this agent, must have at least a 6-month wash-out prior to dosing (Day 1).
10. Is currently taking doxycycline, ursodeoxycholic acid, or taurooursodeoxycholic acid; if previously on any of these agents, must have completed a 30-day wash-out prior to dosing (Day 1).
11. Received prior TTR-lowering treatment (including patisiran) or participated in a gene therapy trial for hATTR amyloidosis.

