6.2.5.1. Cardiac Biomarkers

The cardiac biomarkers NT-proBNP and troponin I will be used to assess cardiac stress and heart failure severity. These biomarkers have been shown to be prognostic of outcomes in HF, including in ATTR amyloidosis.[[Damy 2016](#); [Kristen 2017](#); [Merlini 2016](#)] Blood samples will be drawn to measure cardiac biomarker levels at the timepoints specified in the Schedule of Assessments ([Table 1](#) and [Table 2](#)) and will be measured at a central laboratory. At screening Visit 1, only NT-proBNP will be assessed for eligibility purposes.

Details on cardiac biomarker sample collection, processing, and storage will be provided in a Study Laboratory Manual.

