6.2.5.2. ATTR Amyloidosis Disease Stage

Based on published data from Gillmore et al, the ATTR amyloidosis disease staging used for this protocol stratifies patients with ATTR amyloidosis with cardiomyopathy (both hATTR and wtATTR) into prognostic categories using the serum biomarkers NT-proBNP and eGFR.[[Gillmore 2018](#)] Patients are categorized as follows:

- Stage 1 (lower risk): NT-proBNP \leq 3000 ng/L and eGFR \geq 45 ml/min/1.73 m²
- Stage 2 (intermediate risk): all other patients not meeting criteria for Stages 1 or 3
- Stage 3 (higher risk): NT-proBNP $>$ 3000 ng/L and eGFR $<$ 45 ml/min/1.73 m²

Based on published data, this staging system discriminates between patients with median survival of ~6 years, ~4 years, and ~2 years for Stage 1, Stage 2, and Stage 3, respectively.

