7.2.5. Efficacy Analyses

The overall Type I error rate will be strongly controlled at a 2-sided 0.05 significance level for the primary and secondary endpoints using a fixed sequential testing procedure at the final analysis. The primary endpoint will be compared between treatment arms at the 0.05 significance level. If the test of the primary endpoint is statistically significant, then the secondary endpoints will each be tested in the order specified in the Secondary Endpoints section (see Section 2). If a test of the primary or a secondary endpoint is not statistically significant, the testing of the remaining endpoints in the sequence will stop.

For patients who were tafamidis treatment-naïve at baseline and start tafamidis during the double-blind period, the primary analysis of the primary endpoint will censor data collected after the initiation of tafamidis treatment post-randomization.

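### The Andersen-Gill model for mortality and hospitalisation omits baseline ATTR disease stage; adding it as a prespecified covariate is a free, modest gain in precision

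*Protocol*

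**What the plan says.** Protocol Section 2 lists as the third of three secondary endpoints the "Composite endpoint of all-cause mortality and frequency of all-cause hospitalizations over the 12-month double-blind period". Section 7.2.5 says Type I error is "strongly controlled at a 2-sided 0.05 significance level for the primary and secondary endpoints using a fixed sequential testing procedure", so this endpoint is tested only after the 6-MWT, KCCQ-OS and win-ratio tests have all succeeded.

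Section 7.2.5.2 writes out the model: an "Andersen-Gill model stratified by baseline tafamidis (yes vs no), including treatment, genotype (hATTR vs wtATTR), NYHA Class (I/II vs III") and age below 75 versus 75 or over. Apart from treatment, these are the factors used to stratify randomisation in Section 3.5 (tafamidis, genotype, and NYHA class combined with age). Stage, NT-proBNP and eGFR appear in neither place.

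Section 6.2.5.2 defines stage from NT-proBNP and eGFR and states that "this staging system discriminates between patients with median survival of ~6 years, ~4 years, and ~2 years" for Stages 1, 2 and 3. Of NT-proBNP and troponin I, Section 6.2.5.1 says: "These biomarkers have been shown to be prognostic of outcomes in HF, including in ATTR amyloidosis".

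Eligibility needs both inputs. Inclusion 7 requires "Screening NT-proBNP >600 ng/L and <8500 ng/L" (the Amendment 2 summary lowers the floor to 300 ng/L outside atrial fibrillation). Exclusion 2 removes NYHA III combined with "ATTR amyloidosis disease Stage 3 (defined as both NT-proBNP >3000 ng/L and estimated glomerular filtration rate" below 45. Exclusion 6 removes eGFR below 30, "using the modification of diet in renal disease [MDRD] formula".

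The model text belongs to the Amendment 1 protocol. The Amendment 2 summary adds urgent heart failure visits to this endpoint, excludes COVID-19 deaths and hospitalisations, and lists no covariate change. The part of the file that may hold later wording is not shown.

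**The concern.** In a recurrent-event rate model, a strong prognostic factor left out of the covariates stays in the between-patient variation and so in the robust standard error of the treatment effect. A chance imbalance in that factor between arms is also left uncorrected, here by both design and analysis.

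The primary 6-MWT model carries the baseline 6-MWT value as its severity measure. The Andersen-Gill model has no baseline outcome value; its only cardiac severity measure is a two-level NYHA split. The protocol describes stage as separating survival widely and already collects it. With one year of events and last place in the testing sequence, precision on this endpoint is worth having when it costs nothing.

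**Working it through.** **The plan's own figure.** The only stated power is above 90% for the 6-MWT: N = 300, 1:1, difference 0.7 × 33 + 0.3 × 20 = 29.1 m, SD 75 m, two-sided 0.05. This reproduces: 91.8% at 29 m and 91.9% at 29.1 m. No power, event count or effect size is stated for the Andersen-Gill endpoint.

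**Inputs from the protocol.** Median survival of 6, 4 and 2 years gives exponential hazards ln 2 / 6 = 0.116, ln 2 / 4 = 0.173 and ln 2 / 2 = 0.347 per year, a ratio of 1 : 1.5 : 3. Section 1.3.1.1 gives an earlier-trial placebo rate of 71.8 per 100 patient-years for any hospitalisation or death (0.718 per year).

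**Assumptions, not in the documents.** Stage 1/2/3 shares of 70/25/5, 60/30/10 or 50/35/15; residual frailty variance φ of 0 to 1; rate ratio 0.65.

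**Formula.** With 150 patients per arm and one year, Var(log RR) = Σ over arms of (1/μ + k)/150. With stage in the model, k = φ. Without it, k = φ + CV²(1 + φ), where CV² is the squared coefficient of variation of event rates across stages.

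Worked case (60/30/10, gradient 1:1.5:3, φ = 0.5):
- Mean 0.6 + 0.45 + 0.3 = 1.35; mean square 0.6 + 0.675 + 0.9 = 2.175; CV² = 2.175/1.35² − 1 = 0.193.
- 1/0.718 + 1/(0.718 × 0.65) = 3.5355.
- With stage: (3.5355 + 2 × 0.5)/150 = 0.03024, SE 0.174, power 69.8%.
- Without: k = 0.5 + 0.193 × 1.5 = 0.790; (3.5355 + 1.580)/150 = 0.03410, SE 0.185, power 64.5%.
- Gain 5.2 points.

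**How the gain depends on the hospitalisation gradient** (rate 0.718, RR 0.65):

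| Events that follow stage | Gradient | CV² (60/30/10) | Gain over the three mixes and φ = 0 to 1 |
|---|---|---|---|
| All, at the survival gradient | 1 : 1.5 : 3 | 0.193 | 3.1 to 6.0 points |
| All, more weakly | 1 : 1.2 : 1.7 | 0.035 | 0.5 to 1.3 points |
| Deaths only | 1 : 1.09 : 1.34 | 0.009 | 0.1 to 0.4 points |

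Deaths-only row, 60/30/10: the death rate is 0.6 × 0.116 + 0.3 × 0.173 + 0.1 × 0.347 = 0.156 per year, about 22% of 0.718. The other 0.562 is held equal across stages, giving stage rates of 0.678, 0.735 and 0.909.

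**Simulation of the protocol's model.** Andersen-Gill, N = 300, protocol strata and covariates, with and without stage, gradient 1:1.5:3, robust variance, 1,500 trials per scenario:

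| Rate, RR, mix, φ | Power without stage | With stage |
|---|---|---|
| 0.718, 0.65, 60/30/10, 0 | 75.9% | 79.9% |
| 0.718, 0.65, 60/30/10, 0.5 | 64.3% | 66.7% |
| 0.718, 0.65, 60/30/10, 1 (smallest gain) | 54.8% | 55.7% |
| 0.718, 0.65, 50/35/15, 0 (largest gain) | 74.7% | 80.1% |
| 0.718, 0.483, 60/30/10, 0.5 | 96.0% | 97.4% |

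Gains run from 0.9 to 5.4 points. The variance of log RR falls by about 3% (0.1956²/0.1989² = 0.967) to 8.5% (0.1572²/0.1643² = 0.915). To match this without stage, the trial would need 300 × (1/0.967 − 1) ≈ 10 to 300 × (1/0.915 − 1) ≈ 28 more patients.

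With frailty present, the simulated gain is below the analytic one. The formula credits adjustment with removing CV²(1 + φ), but an independence working model with robust variance removes only CV². In the worked case that gives (3.5355 + 2 × 0.5 × 1.193)/150 = 0.0315, power 68.0%, a gain of 3.4 points. The analytic range is therefore an upper guide.

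**Validity.** Under no effect (60/30/10, φ = 0.5), Type I error with robust variance is 5.0% without stage and 5.3% with it. At RR 0.65 the mean estimates are 0.655 and 0.651. With model-based standard errors, Type I error is 8.9% and 8.5%, and adding stage changes power by −0.6 to +3.0 points. The gain therefore presupposes a robust variance.

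**The case against.** The strongest reply is that the listed covariates mirror the randomisation strata, which is standard practice and explains the age cut. Amendment 1 also shows the sponsor weighing parsimony, since it dropped NYHA class from the 6-MWT model. That stands: the model is a legitimate prespecified choice, and stage would be an improvement on it.

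The second reply is that the 6, 4 and 2 years concern survival, whereas the endpoint also counts every all-cause hospitalisation. It stands too, and it is why the gain must be given as a range that starts near zero. Entry limits also thin out Stage 3, so the upper end needs a stage mix that may not be enrolled.

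Third, a rate ratio of 0.65 puts power in mid-range, where gains look largest. At the earlier trial's own ratio, 34.7/71.8 = 0.483, power is already 96% and the gain is 1.4 points. That trial enrolled hereditary disease with polyneuropathy and the analysis was post hoc, so neither ratio is established here.

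A reader might infer that the protocol calls stage a threefold discriminator of this endpoint, or that power the trial was sized to deliver is being lost. The documents support neither. Threefold is only the Stage 1 to Stage 3 ratio of median survival, and the 300 patients were sized on the 6-MWT alone.

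**Conclusion.** The point holds as a missed efficiency gain. A baseline factor that the protocol describes as strongly prognostic for survival, and measures on everyone before treatment, is absent from a model whose covariates the protocol writes out. The test is valid without it, the estimated rate ratio is almost unchanged, and no stated figure becomes wrong.

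The size is uncertain because the protocol gives no hospitalisation gradient by stage. At a placebo rate of 0.718 and rate ratio 0.65, it runs from under 1 power point if only deaths follow stage, through about 1 point at 1:1.2:1.7, to about 3 to 6 points analytically (0.9 to 5.4 across the simulated scenarios) at the full survival gradient. All of this rests on assumed stage shares and frailty.

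A reader might extend the argument to continuous age, to the 6-MWT and KCCQ-OS models, or to the exploratory death and cardiovascular-event composite. That is not supported here. No gain has been computed for the first two, and Section 7.2.5.3 fixes only descriptive summaries for exploratory endpoints, so it sets no model to amend.

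The conclusion applies to the Amendment 1 wording and assumes, as the Amendment 2 summary suggests, that the covariates have not since changed.

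**What to change.** Before unblinding, add baseline ATTR disease stage as a three-level factor, or log NT-proBNP and eGFR as continuous terms, to the covariates of the Andersen-Gill model in Section 7.2.5.2 and in the SAP. State that inference uses a robust (sandwich) variance, and name the measurement that counts as baseline. Keep the existing stratification and covariates.

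The cost is one sentence and about 2 model degrees of freedom. No new data, visits or patients are needed. First check that the current protocol version still carries the covariate list quoted here.

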7.2.5.3. Exploratory Endpoints

Descriptive summaries will be provided for the exploratory endpoints (Section 2), and additional analyses may be conducted. Details will be described in the SAP.

7.2.6. Pharmacodynamic Analysis

The PD endpoint is serum TTR. Summary tables will be provided for observed values, change and percentage change from baseline for each scheduled time point. In addition, the maximum and mean percentage reduction over 12 months will be summarized.

7.2.7. Pharmacokinetic Analysis

7.2.7.1. Pharmacokinetic Analysis

Plasma concentrations of ALN-18328, DLin-MC3-DMA, and PEG₂₀₀₀-C-DMG will be obtained using a model-independent method. PK exposure parameters will include: maximum plasma concentration at the end of infusion (C_{max}), 30-minute post-infusion concentration ($C_{p(30min)}$), and

pre-infusion concentration (C_{\min}). In addition, the steady-state C_{\max} ($C_{\max,ss}$), steady-state $C_{p(30\text{min})}$ ($C_{p,ss(30\text{min})}$), and steady-state C_{\min} ($C_{\min,ss}$) will be calculated as the average of the respective values at Week 24, Week 36, and Month 12.

The PK exposure parameters will be summarized by visit, and the steady-state PK parameters will be summarized.

7.2.7.2. Exposure-Response Analysis

Mean and maximum percent TTR reduction from baseline will be summarized by quartiles of the steady state PK parameters for all 3 analytes. Change from baseline at Month 12 in clinical efficacy parameters may also be summarized by quartiles of the steady-state PK parameters for all 3 analytes.

PK exposure will be summarized by mortality status. In addition, the incidence of AEs and SAEs will be summarized by quartiles of the steady-state PK parameters for all 3 analytes.

7.2.7.3. Population PK, PK/PD, and Disease Progression Modelling Analysis

Population PK, PK/PD, and disease progression modelling analyses may be performed, if appropriate. If performed, the analyses would be conducted according to a pre-specified analysis plan and reported separately.

7.2.8. Safety Analyses

The primary parameter is the frequency of treatment-emergent AEs (hereafter referred to simply as AEs). Safety parameters also include vital signs, ECGs, clinical laboratory assessments and physical exams. The extent of exposure will be summarized.

Prior and concomitant medications will be coded using the World Health Organization Drug Dictionary. Results will be tabulated by the Anatomical Therapeutic Chemical classification system and Preferred Term (PT).

Adverse events will be classified according to the Medical Dictionary for Regulatory Activities (MedDRA) System Organ Class and Preferred Term. The frequency and percentage of patients experiencing AEs, SAEs, related AEs, and AEs leading to discontinuation will be summarized by System Organ Class (SOC) and PT. By patient listings will be provided for deaths, SAEs, and AEs leading to discontinuation.

Descriptive statistics will be provided for clinical laboratory data, ECG, and vital signs data, summarizing the observed values and change from baseline over time. Laboratory shift tables from baseline at the worst post-baseline values will be presented. Abnormal physical examination findings and 12-lead ECG data will be presented in by-patient listings.

Other safety summaries will be presented as appropriate. Further details will be specified in the SAP.

7.2.9. Immunogenicity Analyses

The frequency and percentage of patients with confirmed positive ADA assay at any time during study as well as at each scheduled visit will be summarized. The titer results for patients with

confirmed positive ADA results will be summarized. The impact of ADA on PK, PD, efficacy and safety endpoints will be explored. Details will be described in the SAP.

7.2.10. Sample Size Re-assessment

Patients who are tafamidis-naïve at baseline may opt to begin tafamidis treatment (ie, “tafamidis drop-in”) during the double-blind period, which could result in a loss of statistical power. An interim assessment may be performed to assess the impact of tafamidis drop-in on the power and the potential need to increase the sample size. The interim assessment, if conducted, would examine the overall tafamidis drop-in rate in a blinded manner (ie, a non-comparative assessment of the drop-in rate); therefore, no impact on the type I error is expected and no multiplicity adjustment will be made. A detailed sample size re-estimation plan will be outlined in a separate document prior to implementation.

7.2.11. Optional Additional Research

Optional additional research may be conducted in the future on the biological samples and/or data collected during the study in accordance with the strict terms of the informed consent form (see Section 4.3.2).

8. STUDY ADMINISTRATION

8.1. Ethical and Regulatory Considerations

This study will be conducted in accordance with the protocol, all applicable regulatory requirements, and the current guidelines of Good Clinical Practice (GCP). Compliance with GCP provides public assurance that the rights, safety, and well-being of study patients are protected consistent with the principles that have their origin in the Declaration of Helsinki.

